1.2 Research Hypothesis

Because current study is an open label trial without placebo control, there is no formal research hypothesis to be statistically validated. The purpose of this study is to test if BMS-986004 will be effective in normalizing platelet counts in subjects with ITP, as well as to assess the safety, PK and immunogenicity of multiple doses of BMS-986004 in ITP subjects.

1.3 Objectives(s)

1.3.1 Primary Objectives

- To assess the overall safety and tolerability of multiple doses of BMS-986004, when administered in subjects with chronic ITP.

1.3.2 Secondary Objectives

- To evaluate efficacy of BMS-986004 in the treatment of thrombocytopenia in subjects with chronic ITP, as measured by platelet response/complete response (R/CR) and other clinical parameters.
- To establish BMS-986004 dose response, as measured by platelet count and other clinical parameters.
- To measure the target engagement of BMS-986004 following multiple IV doses
- To assess the effect of BMS-986004 on markers associated with the risk of thromboembolism (TE) in the multiple dose setting
- To assess pharmacokinetics and immunogenicity of multiple doses of BMS-986004 in subjects with chronic ITP.

[REDACTED]

1.3.4 Long Term Extension Period Objective

- To assess the long term clinical safety, tolerability and efficacy of BMS-986004.

[REDACTED]

1.5 Overall Risk/Benefit Assessment

BMS-986004 is currently being evaluated in humans in a FIH SAD study which is being performed in healthy subjects to investigate the safety, tolerability, PK and PD of BMS-986004. To-date, BMS-986004 has not been studied in the ITP patient population and hence no efficacy or benefit data is established for this population. However, no clinically significant risks have been identified in the FIH study to-date and the safety margins in non-clinical studies are favorable which justifies careful evaluation of BMS-986004 in the ITP patient population. BMS-986004 could potentially provide clinical benefit by normalizing platelet counts in patients with ITP. This study will be initiating at a dose that has demonstrated relatively low immunosuppressive effect and has demonstrated no clinically significant risks in the FIH study. Dose panels will be enrolled sequentially in an ascending manner upon careful review of all cumulative safety information. Cumulative safety data will include all additional data that is available in the FIH study as well as data collected during the ITP study. To manage the safety risks, careful clinical and laboratory monitoring and criteria relative to dose escalation and stopping rules have been established for this protocol and include thresholds for serious infections, liver function tests, platelet counts above established thresholds, and other adverse events.

It is expected that ITP subjects will derive clinical benefit from BMS-986004 and help guide dose selection and design of future studies in the clinical development of BMS-986004. Primary efficacy assessments will include the proportion of patients achieving platelet count at least $\geq 30,000/\text{mm}^3$ and at least 2-fold increase from the baseline count and absence of bleeding.

The subjects planned to be enrolled in this study have limited therapeutic options since they have failed conventional therapies including immunosuppressive therapies, splenectomy and TPO mimetics. It is anticipated that efficacious doses of BMS-986004 will provide long lasting

therapeutic benefit for ITP patients. Ultimately, targeting CD40L may provide opportunity to inhibit autoimmune processes leading to thrombocytopenia and induce durable disease remission. It may thus offer novel therapeutic modality, currently not available to patients.

Given the lack of therapeutic options for ITP subjects who have failed all conventional therapies, BMS-986004 with its distinct mechanism of action and known safety profile appears to have a favorable Risk/Benefit profile.

Detailed information regarding the preclinical toxicology findings based on nonclinical studies in monkeys with BMS-986004 can be found in Section 1.5.2 and the Investigator Brochure.

1.5.1 Potential risks associated with BMS-986004

BMS-986004 is a dimeric anti-human CD40L VH dAb formatted with the Fc-tail from abatacept (modified IgG1) that is entirely inert in Fc effector function, especially in context of FcγRIIIa. All data from nonclinical and NHP studies demonstrate that BMS-986004 exhibited no activity in various platelet activation assays, as well as in direct biacore binding analysis with FcγRIIIa. Based on previous clinical experience with antibodies targeting costimulatory molecules and in particular with anti-CD40L antibodies, potential risks include: (1) increased probability of TE; (2) an increase in susceptibility to infection and (3) immunogenic potential including infusion reactions and formation of ADA. In addition to conventional safety assessments, general risk mitigation plan includes the following:

- To initiate dosing at 75 mg dose that has demonstrated favorable safety profile in healthy subjects in clinical evaluation. This dose is expected to elicit a sub-optimal response while ensuring very good safety profile.
- To utilize safety criteria for intra-subject dose escalation and safety criteria for dose-panel escalation and stopping rules.

1.5.2 Potential Thromboembolic Effect

To continue to mitigate the potential risk of thromboembolism, the following safety measures are included in ITP study:

- Close monitoring of any potential TE activities after BMS-986004 administration. In addition to observing clinical manifestations of both venous and arterial TE, the primary safety biomarkers, d-Dimer and Thrombin anti-Thrombin (TAT), will be monitored to evaluate risk of thromboembolism.
- TE related exclusion criteria have been added to the protocol; patients with history thromboembolic disease (including TIA, stroke, pulmonary embolism, deep vein thrombosis and thrombotic complications) or significant cardiovascular disease (including congestive heart failure, arrhythmias and other conditions known to increase risk of TE) are excluded.

1.5.3 Potential Immunosuppressive effect

As with any novel immunomodulating agent, there is a possibility of reducing normal immune function as a consequence of targeted CD40L blockade and therefore the following safety measures are included in the ITP study:

- Exclusion criteria relative to positive tests for hepatitis B and C, TB and HIV have been included in the protocol.
- Concurrent or recent use of systemic immune-modulating agents is prohibited or restricted to reduce potential risks associated with combinations of immune suppressors.
- Patients will be very closely followed and evaluated for any signs or symptoms of infection and complete blood count (CBC) differential counts, lymphocyte immunophenotyping, and measurement of serum Ig-levels (IgG, IgA and IgM) and CRP will be monitored frequently.

1.5.4 Risk of Infusion Reactions

As with any biological product, infusion reactions are a risk, even following a single dose. To reduce the risk of infusion reactions, patients will be closely monitored by trained personnel experienced with treatment of anaphylaxis and lesser infusion reactions. In addition, IV administration of study drug will not exceed infusion rate of 12.5 mg/min (Table 4-1). Furthermore, patients with history of any significant drug allergy or serious adverse reaction or hypersensitivity to any IV administered biologic will be excluded from the study.

1.5.5 Other

Risks from the PK, PD, and clinical safety phlebotomy procedures are standard and include discomfort at the injection site, bleeding, bruising, and rarely blood clot formation, infection, and fainting. Furthermore, rescue medications are permitted in the study for severe bleeding or wet purpura or if the investigator thinks the patients is at immediate risk. These medications are to be given with the intended purpose of raising platelet counts.

2 ETHICAL CONSIDERATIONS

2.1 Good Clinical Practice

This study will be conducted in accordance with Good Clinical Practice (GCP), as defined by the International Conference on Harmonisation (ICH) and in accordance with the ethical principles underlying European Union Directive 2001/20/EC and the United States Code of Federal Regulations, Title 21, Part 50 (21CFR50).

The study will be conducted in compliance with the protocol. The protocol and any amendments and the subject informed consent will receive Institutional Review Board/Independent Ethics Committee (IRB/IEC) approval/favorable opinion prior to initiation of the study.

All potential serious breaches must be reported to BMS immediately. A serious breach is a breach of the conditions and principles of GCP in connection with the study or the protocol, which is likely to affect, to a significant degree, the safety or physical or mental integrity of the subjects of the study or the scientific value of the study.

Personnel involved in conducting this study will be qualified by education, training, and experience to perform their respective tasks.

This study will not use the services of study personnel where sanctions have been invoked or where there has been scientific misconduct or fraud (eg, loss of medical licensure, debarment).

2.2 Institutional Review Board/Independent Ethics Committee

Before study initiation, the investigator must have written and dated approval/favorable opinion from the IRB/IEC for the protocol, consent form, subject recruitment materials (eg, advertisements), and any other written information to be provided to subjects. The investigator or BMS should also provide the IRB/IEC with a copy of the Investigator Brochure or product labeling information to be provided to subjects and any updates.

The investigator or BMS should provide the IRB/IEC with reports, updates and other information (eg, expedited safety reports, amendments, and administrative letters) according to regulatory requirements or institution procedures.

2.3 Informed Consent

Investigators must ensure that subjects are clearly and fully informed about the purpose, potential risks, and other critical issues regarding clinical studies in which they volunteer to participate.

In situations where consent cannot be given to subjects, their legally acceptable representatives (as per country guidelines) are clearly and fully informed about the purpose, potential risks, and other critical issues regarding clinical studies in which the subject volunteers to participate.

BMS will provide the investigator with an appropriate (ie, Global or Local) sample informed consent form(s) which will include all elements required by ICH, GCP and applicable regulatory requirements. The sample informed consent form will adhere to the ethical principles that have their origin in the Declaration of Helsinki.

Investigators must:

- Provide a copy of the consent form(s) and written information about the study in the language in which the subject is most proficient prior to clinical study participation. The language must be non-technical and easily understood.
- Allow time necessary for subject or subject's legally acceptable representative to inquire about the details of the study.
- Obtain an informed consent signed and personally dated by the subject or the subject's legally acceptable representative and by the person who conducted the informed consent discussion.
- Obtain the IRB/IEC's written approval/favorable opinion of the written informed consent form(s) and any other information to be provided to the subjects, prior to the beginning of the study, and after any revisions are completed for new information.
- If informed consent is initially given by a subject's legally acceptable representative or legal guardian, and the subject subsequently becomes capable of making and communicating his or her informed consent during the study, consent must additionally be obtained from the subject.
- Revise the informed consent whenever important new information becomes available that is relevant to the subject's consent. The investigator, or a person designated by the investigator, should fully inform the subject or the subject's legally acceptable representative or legal guardian, of all pertinent aspects of the study and of any new information relevant to the

subject's willingness to continue participation in the study. This communication should be documented.

The confidentiality of records that could identify subjects must be protected, respecting the privacy and confidentiality rules applicable to regulatory requirements, the subjects' signed ICF and, in the US, the subjects' signed HIPAA Authorization.

The consent form(s) must also include a statement that BMS and regulatory authorities have direct access to subject records.

The rights, safety, and well-being of the study subjects are the most important considerations and should prevail over interests of science and society.

Subjects in this trial will be invited to participate in a voluntary collection for future Medical Research. This collection is encouraged but not mandatory, and subjects who decline to participate will still be allowed to proceed with the rest of the study providing all other conditions are met.

This collection for future Medical Research is intended to expand the translational R&D capability at Bristol-Myers Squibb, and will support as yet undefined research aims that will advance our understanding of disease and options for treatment. It may also be used to support health authority requests for analysis, and advancement of pharmacodiagnostic development to better target drugs to the right patients.

3 INVESTIGATIONAL PLAN

3.1 Study Design and Duration

This is a Phase 1b/2, multicenter, open-label study to evaluate the safety, efficacy, dose response, and pharmacology (PK, target engagement and PD) of BMS-986004 in subjects with ITP.

The study will comprise a short-term period and a long term extension (LTE) period.

The short-term period, is divided into three phases: Response Phase (6 weeks), Remission Phase (6 weeks) and Follow Up phase (8 weeks).

Screening evaluations to determine subject eligibility will be performed 21 days prior to study drug administration. The screening period may exceed 21 days but not more than 42 days total, and only after a discussion with and approval by the Study Director. If an extension in screening time is granted, the patient must still follow the platelet count rules for enrollment. The baseline platelet count determining enrollment eligibility will be based on the mean of two determinations taken within a week of the first dose. To be eligible for enrollment, platelet count needs to be less than $30,000/\text{mm}^3$ and show stable or declining trend. If the mean platelet count is between $30,000 - 35,000/\text{mm}^3$ the subject may be considered for enrollment on a case by case basis after discussion with and approval by the Study Director.

Following screening, a total of 40 evaluable subjects are planned for the study. Subjects are considered evaluable if they receive the first 4 doses of study drug and complete the required

safety and efficacy evaluations at Day 50. Non-evaluable subjects will be replaced to maintain a count of 10 subjects in each dose panels, except subjects will not be replaced if they are discontinued from the study secondary to an adverse event unless the adverse event can be determined to be unrelated to treatment.

Subjects are treated in dose panels of 10 subjects each. Four (4) dose panels are planned to be enrolled sequentially in an ascending manner, with dose intensity selected to provide increased levels of immunosuppression at steady state. Dose levels (range from 75 mg to 1500 mg administered every two weeks) that are planned to be evaluated in this trial are expected to elicit a range of clinical response.

BMS-986004 will be administered once every 2 weeks as an IV infusion for a total of 7 doses. Four (4) doses will be administered during the Response Phase over a 6 week treatment period. The remaining 3 doses will be administered during the Remission Phase of the study over a 6 week treatment period. Subjects will receive investigational product on Day 1/Week 0, Week 2, Week 4, Week 6, Week 8, Week 10 and Week 12, for a total of 7 doses.

Each dose cohort will enroll 10 new subjects, starting with the respective dose level at Day1/Week 0, regardless of the number of subjects joining a dose cohort because of intra-subject dose escalation.

A new cohort may be opened to treat subjects at a dose lower than 75 mg if at least 6 subjects treated at the 75 mg cohort achieve platelet Response (R) (platelet count $\geq 30,000/\text{mm}^3$ and at least 2-fold increase from the baseline count and absence of bleeding), at the end of response phase (Week 6). The new cohort would follow the same schedule as the other cohorts including intra-subject dose escalation.

The **long term extension (LTE)** period is optional and will include eligible subjects from either cohort 3 or cohort 4 who complete 12 weeks (85-days) of treatment and who achieve a response as defined by at least a doubling of platelets from Short Term Day 1 baseline and a platelet count of $\geq 35,000/\text{mm}^3$ and absence of bleeding and any significant AEs as assessed on D71 or if more recent platelet count is available, based on the most recent platelet count or on the average of the two consecutive most recent platelet counts, whichever is higher. If a subject has platelet counts close to a doubling of platelets and/or between 30,000-35,000 platelets/ mm^3 and absence of bleeding and any significant AEs as assessed on D71, the subject may be considered for the long term extension on a case by case basis, which will involve a review of data from the short term period and which will require approval by the Study Director.

3.1.1 Intra-subject dose escalation

Intra-subject dose escalation could occur after the subject has completed the Response Phase of the study. The intra-subject dose escalation decision will be based on review of the safety information and platelet count after 4 weeks of treatment. The decision to escalate dose for the subject will be made after evaluating platelet count at Day 50, 7 days after the 4th dose of BMS-986004 has been administered. Subject will receive the next higher dose of BMS-986004 if clinically significant response has not been achieved based on measurement of platelet count on

the last two consecutive counts performed at Day 43 and Day 50, and a favorable safety profile is observed (see Table 3.1.1-1). Clinically significant response is defined as achieving platelet count $\geq 50,000/\text{mm}^3$ with an increase of at least $20,000/\text{mm}^3$ from baseline and absence of bleeding. Subject will then be dosed at the higher dose level for the remainder of the study (Remission Phase), receiving investigational product at that dose on Week 8, Week 10 and Week 12. Active treatment period with BMS-986004, regardless of the dose, may not exceed 12 weeks for any individual subject.

Table 3.1.1-1: Dose Adjustment after Response Phase

Platelet Count at Day 43 and Day 50 (7 days after the 4th dose) (X /mm³)	Action
< 50,000	Dose increase, as indicated by the next dose panel
$\geq 50,000$ with an increase of at least 20,000 from baseline	Dose remains constant on bi-weekly schedule

3.1.2 Dose frequency adjustment for responders exceeding 450,000/mm³ (for non-splenectomized subjects) and 600,000/mm³ (for splenectomized subjects) platelet count

For both the Short Term Study and the Long Term Extension plan, in the event that platelet count exceeds $450,000/\text{mm}^3$ for non-splenectomized subjects and $600,000/\text{mm}^3$ for subjects who underwent splenectomy, in the absence of recent (administered within two weeks) rescue medication, as indicated by the two consecutive platelet count measurements, dosing of the BMS-986004 should be stopped. Subject will remain in the study and platelet counts will be then assessed based on the normal study visit schedule. Dosing of BMS-986004 could be reinitiated only after discussion between Study Director and Investigator if clinically appropriate and dictated by the medical judgment and subject’s safety.

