- Extremely small probability for β_2 being negative

It is assumed that the response rate at dose of 75mg, 225mg, 675mg, and 1500mg to be 0.2, 0.4, 0.55 and 0.7 respectively. A linear regression using the above data will give prior mean μ to be (-1.33, 0.72) with rounding error. The second and third bullets of the guidelines would make the stand deviation of β_1 to be 0.45, and β_2 to be 0.2. Prior distributions of β_1 and β_2 are assumed to be independent. A 95% credible interval of response rates under prior and without observation data is shown in Figure 1, where the top curve is the upper 97.5% quantile, the center is the mean, and the bottom is the lower 2.5% quantile. The circles represent the expected response rates at the selected doses. It can be seen that the chosen prior would lead to a mean response rate estimate being very close to the expected or assumed, and at the same time the wide region of 95% credible interval indicates that the prior's weak impact on the posterior estimation of response rate when data are observed.

Figure 1: 95% Credible Interval of Response Rate under Prior Only

Special consideration for titration

Non-responders at each cohort other than the maximum 1500mg cohort would be administered higher dose with the hope of becoming responders. Therefore, two response status data may be observed for those non-responders. Due to relative small sample size of each cohort, making use of status data after the titration dose is believed to increase the accuracy of model-based prediction under some reasonable assumptions. Listed in the below are two assumptions used in the adaptive dose selection:

- If a subject responds to a dose, the subject would respond to higher dose with probability 1.

- If a subject does not respond to a dose after 3 administrations, additional dosing at the same dose would not make a subject change from non-responder to responder.

Based on the above assumptions, a new approach is proposed to combine the subjects at two adjacent cohorts to estimate the response rate at the higher dose which is shared by the two cohorts.

Simulation

Trial simulation is done to show the performance of logistic regression and Bayesian logistic regression with starting dose data only or with titration data included. The Settings of simulation parameters are listed below for convenience:

[figure not shown]
- Doses: 75, 225, 675, 1500
- Rate: 0.2, 0.4, 0.55, 0.7

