2 STUDY DESCRIPTION

2.1 Study Design

This is a Phase 1b/2, multicenter, open-label, MAD study to evaluate the safety, efficacy, dose response, and pharmacology (PK, target engagement and PD) of BMS-986004 administered every 2 weeks in subjects with ITP.

Figure 2.1-1: Study Design Schematic

[figure not shown]
The study is divided into screening (3 weeks), response phase (6 weeks), remission phase (6 weeks) and follow up period (4 weeks). Forty subjects are treated in 4 dose panels, 75mg, 225mg, 675mg, and 1500mg, of 10 subjects each. BMS-986004 will be administered on day 1, 15, 29, 43, 57, 71, 85, a total of 7 doses as IV infusion. Four (4) doses will be administered during the Response Phase over a 6 week treatment period. The remaining 3 doses will be administered during the Remission Phase of the study over a 6 week treatment period. The study design schematic is presented in Figure 2.1-1.

Cohort of lower than 75mg or intermittent dose may be opened.

Intra-subject dose escalation

Subject may be dosed at a higher dose beginning from day 57 for the remainder of the study if clinically significant response has not been achieved at Day 43 and Day 50, and a favorable safety profile is observed.

Figure 2.1-2: Decision Rule on Intra-Subject Dose Escalation

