7.5.1 Derivation of Efficacy Endpoints

Primary efficacy criteria and response category:

- Response (R) - platelet count $\geq 30,000/\text{mm}^3$ and at least 2-fold increase from the baseline count and absence of bleeding.
- Complete Response (CR) - platelet count $\geq 100,000/\text{mm}^3$ and absence of bleeding.
- No Response (NR) - platelet count $< 30,000/\text{mm}^3$ or less than 2-fold increase of baseline platelet count or bleeding.
- Not Assessable (NA) - platelet count is missing or is excluded due to rescue medication.

Subject's best response is decided in the order of CR, R, NR, and NA.

Secondary efficacy criteria and response category:

- Clinically Significant Response - platelet count $\geq 50,000/\text{mm}^3$ with an increase of at least $20,000/\text{mm}^3$ from baseline and absence of bleeding.
- No Clinically Significant Response - platelet count $< 50,000/\text{mm}^3$, or increase of $\leq 20,000/\text{mm}^3$ from baseline, or bleeding.
- Not Assessable (NA) - platelet count is missing or is excluded due to rescue medication.

Absence of bleeding:

Absence of bleeding is defined as SMOG scores being zero for all the three major domains (Skin, visible mucosae, and organs) with ITP-BAT on the same day when platelet count is assessed.

Platelet data exclusion and rescue medication flag:

Platelet counts collected within 4 weeks after any rescue medication, though still shown in listing of figures of raw data, will be excluded from summarizing platelet and deriving subject response. To facilitate the exclusion, rescue medication flag may be derived and included in some analysis datasets and listings if at least one subject takes rescue medication after the first dosing during the trial. Rescue medication flag is set to Y (Yes) within 4 weeks after the day any rescue medication is administered, i.e., between rescue medication day and rescue medication day + 27, inclusively. It will be set to N (No) when otherwise.

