7.5.2 Bleeding Score - SMOG

Bleeding, as measured by ITP-BAT SMOG, will be listed for all treated subjects. Due to the nature of the incremental assessment of ITP-BAT, evaluation period (start day and end day) will be provided. Start day of an assessment is the end day of the immediately previous assessment visit. Start day would be missing for the first bleeding assessment (screening visit).

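### Section 3.1.1 and its own Table 3.1.1-1 give opposite Day 57 dose instructions for a subject whose platelet counts qualify but who has bleeding and a safety profile still judged favorable

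*Protocol*

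**What the plan says.** Protocol Section 3.1.1 states the rule in prose: "Subject will receive the next higher dose of BMS-986004 if clinically significant response has not been achieved", judged on Days 43 and 50, "and a favorable safety profile is observed (see Table 3.1.1-1". The next sentence defines the response by a count of at least 50,000/mm³ and a rise of at least 20,000/mm³, and ends "from baseline and absence of bleeding. Subject will then be dosed at the higher dose level". Bleeding is therefore part of the definition on which the dose turns.

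Table 3.1.1-1 has two rows, both in platelet terms. Counts below 50,000 lead to an increase to the next panel's dose. For counts of at least 50,000 with a rise of at least 20,000 the action is "Dose remains constant on bi-weekly schedule". Neither row mentions bleeding.

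The synopsis repeats the three-part definition. SAP Section 2.1 allows a higher dose "if clinically significant response has not been achieved at Day 43 and Day 50, and a favorable safety profile is observed". SAP Section 7.5.1 classes bleeding as no clinically significant response and adds: "Absence of bleeding is defined as SMOG scores being zero for all the three major domains".

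**The concern.** The text and the table it cites should give the same dose for every subject. For one kind of subject they do not, and nothing readable in either document says which governs. A site working from the table and a site working from the prose would treat the same subject differently, and the difference is a full dose step in a study whose primary objective is safety.

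There is a smaller effect on the dose-response data. Appendix 2 proceeds on the footing that "Non-responders at each cohort other than the maximum 1500mg cohort would be administered higher dose with the hope of becoming responders". A subject held at the starting dose under the table, though a non-responder under the SAP's secondary criteria, would have no outcome at the higher dose.

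**Working it through.** This is a comparison of two rules; the plan gives no figure to reproduce.

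**Inputs.** Text rule and definition: Protocol Section 3.1.1. Table rule: Table 3.1.1-1. Dose levels of 75, 225, 675 and 1500 mg: Protocol Table 4-1. Baseline limits: inclusion criterion 2d (mean below 30,000, or 30,000 to 35,000 with case-by-case approval). Bleeding is scored by ITP-BAT at Day 43 and Day 50 (Table 5.1-2), so the bleeding condition can be applied on both days.

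**Rules.** Let C be the count on a decision day and B the baseline.
- Response = (C ≥ 50,000) and (C − B ≥ 20,000) and no bleeding.
- Text: increase if Response is missed and safety is favorable; otherwise do not increase.
- Table: increase if C < 50,000; hold if C ≥ 50,000 and C − B ≥ 20,000.

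**Results**, with the same count and bleeding status on both days and a starting dose below 1500 mg:

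| Baseline | Count | Rise | Bleeding | Safety | Text | Table |
|---|---|---|---|---|---|---|
| 15,000 | 40,000 | 25,000 | no or yes | favorable | increase | increase |
| 15,000 | 60,000 | 45,000 | no | favorable | hold | hold |
| 15,000 | 60,000 | 45,000 | yes | favorable | **increase** | **hold** |
| 15,000 | 60,000 | 45,000 | yes | not favorable | no increase | hold |
| 34,000 | 52,000 | 18,000 | no | favorable | increase | no row |

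The third line is the contradiction. The fourth shows its limit: once the safety profile is judged unfavorable, neither rule raises the dose.

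**Size of the dose step.** 225/75 = 3; 675/225 = 3; 1500/675 = 2.22.

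**The missing row.** A count of at least 50,000 with a rise below 20,000 needs 50,000 − B < 20,000, so B > 30,000. At B = 35,000 the uncovered counts run from 50,000 to below 35,000 + 20,000 = 55,000. This is a narrow range, open only to subjects enrolled by case-by-case approval.

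**Day 43 against Day 50.** Suppose both counts qualify and bleeding is recorded on Day 43 only. If the response must be missed on both days, the text holds the dose and agrees with the table. If missing it on either day is enough, the text increases and the conflict appears. The wording allows both readings. SAP Section 7.5.2 says "Start day of an assessment is the end day of the immediately previous assessment visit", so under SAP conventions a bleed between Day 29 and Day 43 counts at Day 43. Whether it affects the dose still depends on this unresolved point.

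**The case against.** The best defense is that a platelet-only dose rule is intended. Section 3.1.1 says the judgment rests on the platelet counts of Days 43 and 50, and the table is headed by platelet count. However, the definition in the next sentence includes bleeding, as do the synopsis and SAP Section 7.5.1. If platelets alone should decide, the prose is what needs correcting; the two parts still disagree.

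Second, a bleeding subject may be judged to have an unfavorable safety profile, and then there is no conflict. This stands as a limit. It does not remove the case: if absence of bleeding is read as in the SAP, any non-zero skin, mucosal or organ score defeats response, and minor skin bleeding in ITP need not make the drug's safety profile unfavorable. The SAP wording is an endpoint derivation, though, and is not stated as the investigator's dosing criterion.

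Third, Protocol Figure 3.1.3-2 and SAP Figure 2.1-2 concern this same decision and are not shown. They may side with either version. They could settle the intent, but the text and its table would still differ.

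A reader might also infer more than the documents support:
- **A count of affected subjects.** One could multiply Appendix 2's response rates by a bleeding share. No bleeding share is given. The protocol's primary response already requires absence of bleeding and uses a different platelet threshold, so those rates may exclude the very subjects in question. The favorable-safety condition and the two-day ambiguity would also have to be allowed for.
- **A second contradiction, because the table has no safety criterion.** The sentence citing the table already carries that condition.
- **A distorted early-escalation rule.** nH counts subjects actually titrated, so it is correct whichever instruction was followed.
- **A defect in the Section 3.1.3 hold.** Those rules are written for opening the next cohort; whether they also bind individual Day 57 increases is a separate question of interpretation.

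**Conclusion.** The contradiction is real but narrow. It needs a starting dose below 1500 mg, both platelet conditions met, bleeding that defeats clinically significant response, and a safety profile still judged favorable. For that subject the text gives a 3-fold or 2.2-fold increase and the table gives none. Among the readable sources the table is the outlier, subject to the two figures that could not be checked.

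Only the three planned cohorts below 1500 mg, 30 of 40 subjects, can be titrated. How many would fit the profile cannot be estimated from the documents, and it is probably few. The effect on analysis is limited: non-PK summaries go by starting dose (SAP Section 6.2), the Day 57 dose is reported per subject (SAP Section 7.5.4), and model-based dose selection is optional. The reason to act is that a dosing instruction is wrong as written and cheap to correct. The missing row is minor, because the text already decides that case as an increase.

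**What to change.** Reword Table 3.1.1-1 in the terms that Section 3.1.1 already defines:
- Row 1: *Clinically significant response (as defined in 3.1.1, including absence of bleeding) not achieved, and favorable safety profile: increase to the dose of the next panel.*
- Row 2: *Clinically significant response achieved, or safety profile not favorable: dose is not increased.*

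This also closes the gap for a rise below 20,000. Add one sentence to Section 3.1.1 stating whether the response must be missed on both Day 43 and Day 50 or on either day, and check that the two decision figures match.

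If the sponsor intends platelets alone to decide the dose, correct the prose of Section 3.1.1 and the synopsis instead, give that rule its own name, and align the description in SAP Section 2.1. The SAP endpoint, with its bleeding condition, should stay as it is.

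Under the first option the cost is two table rows and one sentence in the protocol, with the same day clarification carried into SAP Section 2.1 if wanted. Visits, sample size, nH and endpoint definitions do not change.
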